**INSTRUCTIONS**

This template is intended to help investigators prepare a protocol that includes all of the necessary information needed by the IRB to determine whether a study meets approval criteria. **Read the following instructions before proceeding:**

1. Use this protocol template for a PI initiated study that includes direct interactions with research subjects. Additional templates for other types of research protocols are available in the system Library.
2. If a section or question does not apply to your research study, type “Not Applicable” underneath.
3. Once completed, upload your protocol in the “Basic Information” screen in IRES IRB system.

## SECTION I: RESEARCH PLAN

### 1. Statement of Purpose:

State the scientific aim(s) of the study, or the hypotheses to be tested.

We plan to conduct a randomized, controlled trial to determine the impact of the Apple Watch Series 6 on both patient-reported outcomes and clinical utilization over 1 year. Our research method will employ a patient-centered health data-sharing platform (called Hugo) for real-world surveillance of outcomes in 150 total patients after they receive direct current cardioversion (DCCV) or catheter ablation for treatment of atrial fibrillation or atrial flutter. We will recruit a total of 150 patients across 3 clinical sites- 60 at Yale-New Haven Hospital, 60 at the Mayo Clinic, and 30 at Duke Health- before they undergo DCCV for atrial fibrillation or atrial flutter or after they undergo catheter ablation for atrial fibrillation or atrial flutter. Half of the patients will be randomized to receive the Apple Watch Series 6, while half will receive a control device (Withings Move). Patients will then be queried about specific symptoms related to atrial fibrillation and medication adherence monthly for a total of 6 times post-procedure (6 months) and also at 12 months. This project will provide novel and needed post-market data about the recently cleared Apple Watch Series 6 ECG and irregular rhythm detection notification features and, on a larger scale, help delineate the impact of an innovative digital health technology on real-world patient outcomes.

**Specific Aim 1:** To assess the impact of using the Apple Watch ECG and irregular rhythm notification features on patient-reported outcomes and clinical utilization after patients receive cardioversion or catheter ablation for atrial fibrillation or atrial flutter.

**Specific Aim 2:** To determine the accuracy of the Apple Watch ECG compared to physician interpretation of 12-lead ECGs obtained in routine clinical care.

### 2. Probable Duration of Project:

State the expected duration of the project, including all follow-up and data analysis activities.

The project is expected to be completed no later than June 2024 with enrollment beginning August 2021. Monitoring of each patient lasts a total of 12 months post-procedure. As batches of patients complete the 6-month follow-up duration, we will begin to clean and review the data on a rolling basis. We will examine data for 1 year after enrollment.

### 3. Background:

Describe the background information that led to the plan for this project. Provide references to support the expectation of obtaining useful scientific data.

The pace of innovation for digital health technologies is accelerating. Many novel technologies employ software as a medical device and enable consumers to access their own health data in previously unimaginable ways. Simultaneously, the Food and Drug Administration (FDA) is establishing a nimble, least burdensome regulatory framework for such technologies under its Digital Health Innovation Action Plan. For software-based medical devices, the agency has initiated a Software Precertification (Pre-Cert) Pilot; a key element is collecting and interpreting post-market, real-world data about software performance. In September 2018, FDA cleared 2 software features for the Apple Watch: 1) to detect irregular heart rhythms likely to be atrial fibrillation and 2) to generate a single-lead ECG. However, several risks were identified, including: misinterpretation and/or over-reliance on the device, false negatives, and false positives; mitigation strategies were also identified. Similar consumer digital technologies and software applications are growing in use and increasingly brought to FDA for clearance as medical devices. Therefore, there is a need to assess

the clinical impact of these devices through active surveillance to guide future labeling and risk mitigation strategies. Further, there are discussions to bring the Apple Watch to Medicare beneficiaries.

Therefore, we have planned a multi-center, post-market randomized, controlled trial to understand the safety and effectiveness of the Apple Watch ECG and irregular rhythm notification features on patient-reported outcomes and clinical utilization in real-world patients receiving cardioversion or catheter ablation for atrial fibrillation or atrial flutter. Patients receiving cardioversion or catheter ablation for atrial fibrillation or atrial flutter will be randomized to receive the Apple Watch Series 6 or the Withings Move used as a control device. Using a patient-centered health data-sharing platform for data collection and aggregation, we will monitor patient quality of life for 12 months. We will also examine additional treatment for atrial tachyarrhythmias and how clinical utilization differs between the 2 groups. Finally, we will assess the Apple Watch's ability to serve as a tool for post-market ECG surveillance monitoring by examining its accuracy compared to physician interpretation of 12-lead ECGs obtained in routine clinical care. This study is funded by the National Evaluation System for health Technology Coordinating Center (NESTcc) and advances the use of real-world data generation in peoples' home environments and the use of routinely collected clinical data to support safety and effectiveness evaluations.

Of note, we will be leveraging infrastructure from a recently-completed study for this work. We recently completed a 60-patient study conducted by the Yale-Mayo Clinic FDA Center for Excellence in Regulatory Science and Innovation, of which 30 patients were enrolled at Yale-New Haven Hospital (IRB Protocol #2000021455), YNHH Principal Investigator: [name], MHS, which pilot tested the feasibility of using the Hugo Health platform for post-market surveillance of patients after either catheter-based atrial fibrillation ablation or bariatric surgery. Thirty additional patients were enrolled at Mayo Clinic.

4. **Research Plan:** Summarize the study design and research procedures using non-technical language that can be readily understood by someone outside the discipline. **Be sure to distinguish between standard of care vs. research procedures when applicable, and include any flowcharts of visits specifying their individual times and lengths.** Describe the setting in which the research will take place.

#### Overall Study Design

This will be a prospective multi-center, randomized, controlled trial of 150 patients conducted to assess the impact of individual use of the Apple Watch on patient-reported and clinical outcomes at 1 year. Sixty of these patients will be recruited at Yale-New Haven Hospital. This sample size was calculated assuming 80% power to detect an effect size of 8.8 on the AFEQT questionnaire (slightly higher than the minimal clinically important difference of 5), with alpha 0.05. Additionally, we will validate Apple Watch Series 6 ECG readings when a simultaneous 12-lead ECG is obtained in clinical practice; the purpose of this validation is to assess the Apple Watch's ability to serve as a heart rate and ECG monitoring tool that may be used for periodic rhythm checks in post-market surveillance of other medical products (such as catheters used for atrial fibrillation ablation or antiarrhythmic medications).

#### Enrollment Procedure

As part of routine practice, outpatients who are planned to undergo cardioversion for atrial fibrillation or atrial flutter at Yale-New Haven Hospital will be contacted via phone by the department scheduler to confirm their scheduled time for their procedure. At this time the scheduler will tell the patient he/she may be eligible for a study examining the impact of using a wearable digital health device following cardioversion and then

ask about interest in the study (Please see appendix for script). Should they express interest, the scheduler will let them know that a Research Associate (RA) may reach out to them in advance of their procedure to discuss the study in further detail. The scheduler will then provide the RA with the patient's preferred contact information.

Once the patient has expressed interest in the study, the RA will open the patient's chart to ensure that the patient has a history of atrial fibrillation or atrial flutter before calling the patient. If there is not a confirmed diagnosis in the chart, the RA will confirm with a study clinician. The RA will attempt to contact the patient by phone in advance of their procedure. The RA will then use a checklist to confirm the patient meets all of the eligibility criteria (see below), including asking if they receive primary and cardiology care in the Yale-New Haven Health System. If the patient does not receive primary care in the Yale-New Haven Health System, the RA will ask the patient a) where they receive primary care and b) if they have a patient portal account for that provider. If the patient has a portal account for their primary care provider and that provider uses an Epic- or Cerner-based EHR, they are eligible for this study. If they do not, they will be considered ineligible. The RA will then review the process with the patient and inform him/her that participation is optional but if they would like to learn more and possibly enroll, they should arrive 60 minutes before their scheduled arrival time to meet and go through the consent and enrollment process. The RA will also ask the patient to bring his/her smartphone and YNHH MyChart login information (if they have it) and any phone account passwords with them that day, as well as advising them to update their device to the latest iOS if they have not done so already. The RA will be able to provide guidance on updating the device, if necessary.

A member of the clinical team may also introduce the study to eligible patients. If the patient expresses interest in being contacted, a member of the office staff will provide the RA with the patient's preferred contact information.

If a member of the clinical team identifies a patient that has been admitted to the hospital and will undergo DCCV in the next 24-48 hours, that patient would qualify for this study and the study clinician will inform the RA about the patient. The RA will then approach the patient and use a checklist to confirm the patient meets all of the eligibility criteria (see below). The RA will then review the study with the patient and inform him/her that participation is optional but if they would like to learn more and possibly enroll the RA will walk through the consent and enrollment process with them. The RA will be able to provide guidance on updating the device, if necessary.

On the day of the anticipated cardioversion, or the day prior for inpatients, the RA will then review the study consent form and discuss the specifics of the study described below. If, after reviewing, the patient agrees to the study, then he/she will be asked to sign the digital consent and authorization form for YNHH in the Hugo platform.

Separately, patients undergoing catheter ablation for atrial fibrillation or atrial flutter will be informed about study eligibility by their physician. As with cardioversion patients, the RA will attempt to contact the patient by phone in advance of their procedure. The RA will then use a checklist to confirm the patient meets all of the eligibility criteria (see below), including asking if they receive primary and cardiology care in the Yale-New Haven Health System. If the patient does not receive primary care in the Yale-New Haven Health System, the RA will ask the patient a) where they receive primary care and b) if they have a patient portal account for that provider. If the patient has a portal account for their primary care provider and that provider uses an Epic- or Cerner-based EHR, they are eligible for this study. If they do not, they will be considered ineligible. The RA will then review the process with the patient and inform him/her that participation is optional but if they would like to learn more and possibly enroll, they will have the option after their ablation, on the first post-

procedure day. If the patient is interested and eligible, the RA will ask the patient to bring his/her smartphone and YNHH MyChart login information (if they have it) and any phone account passwords with them that day, as well as advising them to update their device to the latest iOS if they have not done so already. On the first post-procedural day, patients will be approached by the RA to assess and ensure patients meet inclusion criteria and are interested in study participation. The RA will use a checklist to confirm the patient meets all of the eligibility criteria (see below). The RA will then review the study with the patient and inform him/her that participation is optional but if they would like to learn more and possibly enroll the RA will walk through the consent and enrollment process with them. The RA will be able to provide guidance on updating the device, if necessary.

We will ensure that the patient has a full and clear understanding that enrollment will not in any way impact his/her care nor alter the standard post-procedure follow-up visits. As a part of the consent process, the RA will also make clear to the patient that this study will not replace their normal medical care and advise him/her that should they begin having new or worrying symptoms to contact their doctor or emergency services directly, exactly as the patient would have done if he/she were not enrolled in our study. During enrollment the patient will also confirm their preferred contact method should the RA need to reach them during or after the follow-up period. Patients can indicate if they prefer text, email, and/or phone calls. In addition to their preferred method, we will ask them if they would be willing to be contacted by each modality. Should they indicate text or phone calls, the RA will offer to enter or suggest that the patient enter, the RA's Yale office number into their contact list so that they are aware when it is the study staff trying to reach them.

The RA will then assist the patient in linking his/her YNHH electronic health records to the Hugo platform. This linkage enables the patient to share all of the data available as part of their electronic health record data via their patient portal, with our researcher team. Because the patient-centered health data-sharing platform (Hugo) obtains patient data through patient portals, all patients who connect will need a YNHH MyChart account. The RA will assist the patients in creating a MyChart account if they do not already have one. Once the patient has completed the MyChart sign-up process, then the RA will assist the patient in creating and activating an account for the mobile health platform, Hugo, on either the study laptop or on the patient's personal smartphone depending on the patient's preference. Some patients may need to reset their MyChart password, and the RA will help them to do so. The RA will also assist the patient in connecting any other health systems found in the Hugo platform where they have received care by showing the study participant how to enter their patient portal credentials; for patients who receive primary care outside of YNHH but within an Epic- or Cerner-based electronic health record, we will ensure that patients connect data from that health system. Patients will receive a digital version of the 20-item Atrial Fibrillation Effect on QualiTy-of-life (AFEQT) questionnaire via email or text message (per patient preference); this questionnaire assesses symptoms, daily activities, treatment concern, and satisfaction.

At this time, the patient will be randomized 1:1 to the Apple Watch or control (Withings) arm using a central randomization algorithm. Patients randomized to the former will receive an Apple Watch Series 6 (WiFi/GPS) or a Withings Move. For Apple Watch patients, an Apple HealthKit account will be set up and linked to the Hugo platform; they will also need to install the Hugo App for iPhones which will enable receipt of Apple Watch-related data. Patients randomized to a Withings Move will be assisted in setting up a Withings Health Mate account, which will be linked to the Hugo platform. While setting up the Apple Watch application, RAs will assist patients in answering that they have not been previously diagnosed with atrial fibrillation (as enrichment of the study population with people likely to have recurrent atrial fibrillation and/or atrial flutter is necessary to understand how this device functions in people diagnosed with atrial fibrillation and/or atrial flutter).

We will also ask the patients to self-report their sex, race, ethnicity, and their preferred contact method. We will also ask if they have any of the following co-morbidities: arrhythmias other than atrial fibrillation or atrial flutter (and ask them to report which one(s), if any), hypertension, diabetes mellitus, high cholesterol, sleep apnea, coronary artery disease (including myocardial infarction/heart attack), heart failure, stroke, weak or failing kidneys, any liver condition, cancer, asthma, emphysema, depression, PTSD, or generalized anxiety disorder.

For patients undergoing cardioversion, the RA will attempt to complete all of the enrollment steps before the patient's procedure (cardioversion). Review of and signing of the consent will always be required prior to the procedure. In order to not impact the clinical workflow, some enrollment procedures may be completed post-operatively, if necessary, due to time constraints. If any part of enrollment needs to be completed post-procedure, the RA will always wait a minimum of 20 minutes after the patient is brought into recovery to allow any sedatives to wear off and confirm with the post-op nursing staff that the patient is awake, and that it is acceptable to approach them. Before proceeding with any enrollment procedures, the RA will then confirm the patient is alert and oriented by asking the patient to confirm their name, why they are in the hospital, and what city they are currently in. They will be asked to confirm that they recall the study and are amenable to continuing the enrollment process. The RA will aim to only have items such as syncing the devices to the phone and/or connecting any portal to Hugo, to be completed after the procedure. The baseline survey will be prioritized to be completed, after informed consent, pre-procedure.

For patients who had undergone catheter ablation for atrial fibrillation or atrial flutter, all enrollment procedures will occur only on the first post-procedural day, when the patient is generally recovering and awaiting discharge.

Of note, even though the Apple Watch Series 6 device is not intended for use in individuals previously diagnosed with atrial fibrillation, the ECG feature is not recommended for users with arrhythmias *except* for atrial fibrillation and sinus rhythm (since the software can only distinguish these two heart rhythms). People with atrial fibrillation may be more likely to purchase this device than others to monitor their rhythm and correlate with symptoms. Indeed, in the Apple Heart Study, nearly 20% of first study visit participants reported a diagnosis of atrial fibrillation/flutter before enrollment, even though a history of atrial fibrillation was an exclusion criterion. Few digital health studies have enrolled patients with clinical morbidities to examine outcomes; such studies have instead focused on healthy volunteers. Our study will address this limitation. Additionally, a study examining the impact of the Apple Watch on patient-reported outcomes and clinical utilization requires an enriched population; otherwise, study duration would be many years with a population size multiples larger than our proposal, resulting in significant cost and delays in generating much-needed evidence.

For patients undergoing cardioversion, if there is time before the cardioversion and always after the cardioversion, we will ask the patient to obtain an ECG using the Apple Watch Series 6 (and the RA will assist the patient if needed), with the 10-second interval that has the best resolution and is free from artifact for comparison to the interpretation of a 12-lead ECG obtained for clinical care (as these are 10 seconds long). If possible, we will also ask the patient to take a SpO2 reading while the RA is present and they are connected to a standard, medical grade pulse oximeter in the clinical setting.

A separate survey, both for patients undergoing cardioversion and who received catheter ablation for atrial fibrillation or flutter, will be sent at enrollment asking patients, only with the help of study staff, to enter both their Apple Watch pulse oximeter reading and the reading taken using a medical grade SpO2 monitor.

The RA will record the total time (minutes) for enrollment of each patient, including: device and account setup, in-person consenting, baseline survey (if the RA is present), ECG measurement (if performed) and SpO2 measurement (for Apple Watch patients). The RA will record a total time, and segment the times into discrete enrollment steps, if possible. The RA will not record time that the RA is not with the patient (for example, when the patient is undergoing cardioversion). The RA will also record enrollment type (inpatient or outpatient, with all patients undergoing catheter ablation considered inpatients) within Hugo. After enrollment, patients will also receive a follow-up email that contains their consent form as well as to again provide contact information should they have any questions or concerns about the study.

If a patient refuses to participate, then we will note the number of people who refused. If the patient is agreeable, we will then administer a short questionnaire to understand his/her rationale for not participating in the study, to understand potential reasons for non-participation. Please see Appendix for questionnaire.

If for any reason, portal and/or device connections cannot be completed at the time of enrollment (i.e., there is not enough time to complete, patient does not have their passwords with them, etc.), the RA will follow up with the patient via phone to finish the connections. Up to 3 attempts will be made to contact the patient. If there is no response via phone, the study team will send a letter via postal mail, asking the patient to complete their connections.

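### The number of AF pairs for Aim 2 is uncontrolled: the watch ECG before cardioversion is conditional, and rhythm agreement is not reported by rhythm

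*Protocol*

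**What the plan says.** The second specific aim (Protocol, Section I, item 1) is "To determine the accuracy of the Apple Watch ECG compared to physician interpretation of 12-lead ECGs obtained in routine clinical care".

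The pairings come from four places in the Protocol:

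- **Cardioversion day** (Enrollment Procedure): "if there is time before the cardioversion and always after the cardioversion, we will ask the patient to obtain an ECG" with the watch.
- **Ablation patients** (same section): "all enrollment procedures will occur only on the first post-procedural day". No pre-procedure pair is possible for them.
- **Follow-up** (Follow-Up): watch-arm patients are asked to record a watch ECG each time they have an ECG in routine care, over 12 months.
- **Month 6** (Follow-Up): a final watch ECG is requested, with no 12-lead tied to it.

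The Enrollment Procedure describes the steps in this order: consent, MyChart and Hugo linking, AFEQT, randomisation, then issue and set-up of the watch. For cardioversion patients the default is that "the RA will attempt to complete all of the enrollment steps before" the procedure. If time is short, the research associate aims to leave only "items such as syncing the devices to the phone and/or connecting any portal to Hugo, to be completed after the procedure". What is protected is the questionnaire: "The baseline survey will be prioritized to be completed, after informed consent, pre-procedure". When the time spent on enrolment is recorded, the ECG is listed as a step that may or may not have been performed.

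For analysis, the Protocol (Secondary Clinical Outcomes; item 12) and SAP 1.6.2 score rhythm as identical to the 12-lead or different. Neither plans agreement separately by rhythm, and neither sets a number of pairs or a precision for Aim 2.

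**The concern.** A patient about to be cardioverted is expected to be in AF or flutter; afterwards sinus rhythm is the usual expectation. The plan thus makes the more informative pairing for AF detection optional and always requests the less informative one. The step order adds to this, because the watch is handed over late in the sequence and its syncing is a named candidate for deferral.

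AF detection matters to this aim. The Protocol (Overall Study Design) wants to know whether the watch can serve for periodic rhythm checks when other products, such as ablation catheters, are under surveillance. Item 9 (Risks) lists false negatives among the recognised risks. If most pairs are in sinus rhythm, a single same-or-different percentage mainly measures recognition of sinus rhythm, and a watch that misses AF can still score well. Pairs that were never recorded cannot be recovered in analysis.

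**Working it through.** **1. The plan's own figure.** The only sample size in the documents is 150, for AFEQT. With a difference of 8.8, SD 18.5 (SAP 1.4), two-sided alpha 0.05 and 80% power:

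n per arm = 2 × (1.960 + 0.842)² × 18.5² / 8.8² = 69.4, so 70.

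Allowing for 8% non-completion, 70 / 0.92 = 76.1, so 77 per arm or 154 in total, close to 150. The figure is reproduced, but it concerns Aim 1 and says nothing about ECG pairs. What Aim 2 takes from it is the watch arm: 150 / 2 = 75 patients.

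**2. What the documents leave open.** They give no usable cardioversion/ablation split (item 5 describes the 60 Yale participants as cardioversion patients, while other sections admit ablation patients). They also give no share of patients with time before the procedure, no rate of sinus rhythm afterwards, no recurrence rate and no number of routine ECGs. Every input below except the 75 is an assumption.

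**3. Post-procedure pairs alone.** AF/flutter pairs = k × (1 − s), where k is the number of watch-arm cardioversion patients and s the share in sinus rhythm afterwards.

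- k = 25, s = 95%: 25 × 0.05 = 1.25
- k = 40, s = 90%: 40 × 0.10 = 4
- k = 60, s = 80%: 60 × 0.20 = 12

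Take the middle case and treat all 4 as AF. If the watch reads the 36 sinus pairs correctly and misses all 4 AF pairs, agreement is 36/40 = 90%. If it reads all 4 correctly, the exact (Clopper-Pearson) lower limit is 0.025^(1/4) = 0.398, so the 95% CI is 40% to 100%.

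**4. Pre-procedure pairs under the current wording.** Pairs = 75 × cardioversion share × share with time.

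| Cardioversion share | Time in 10% | Time in 75% | Always obtained |
|---|---|---|---|
| 25% | 2 | 14 | 19 |
| 50% | 4 | 28 | 38 |
| 75% | 6 | 42 | 56 |
| 100% | 8 | 56 | 75 |

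These are AF or flutter pairs, so the AF count is lower by the number in flutter.

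**5. Follow-up AF pairs.** Pairs = 75 × routine ECGs per patient × share in AF × compliance.

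- Low: 75 × 1 × 0.10 × 0.25 = 1.9
- Middle: 75 × 2 × 0.20 × 0.50 = 15
- High: 75 × 4 × 0.30 × 0.75 = 67.5

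**6. Precision for AF detection at about 90% correct (exact 95% CI).**

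- 8 of 9: 52% to 100%
- 17 of 19: 67% to 99%
- 34 of 38: 75% to 97%

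The range runs from a handful of AF pairs, too few for a useful estimate, to several dozen. Nothing in the plan determines where in that range the trial will fall.

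**The case against.** A reader might infer that Aim 2 will contain very few AF pairs. The documents do not support that. The default is to attempt every enrolment step beforehand; deferral is the fallback. Outpatients are asked to come 60 minutes early, and inpatients may go through consent the day before. Routine-care pairs accrue for 12 months in a population deliberately enriched for recurrence. A very small count is only the low end of the ranges above.

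Nor is it right to say that the post-procedure ECG is always done: the text says patients are always asked. It would also be unfair to set 4 AF pairs under the current plan against 40 under a revised one. That credits the current plan with no pre-procedure or follow-up pairs, assumes complete capture after the change, and counts flutter as AF. The Protocol itself says the software distinguishes only AF and sinus rhythm, so a flutter pair does not measure AF detection.

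Sinus pairs are useful too. They inform false positives, heart rate and the intervals, and PR cannot be measured in AF.

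All of this stands, and it limits the claim to a count that is uncontrolled and possibly small. It does not remove the asymmetry in the wording, the late place of the watch in the sequence, or the lack of any analysis by rhythm. The follow-up pairs help only if a patient happens to be in AF at a routine ECG, wears the watch, records an ECG unprompted by staff, and the tracing reaches the study.

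**Conclusion.** The point holds in a limited form. The one protocol-timed pairing at which AF or flutter is expected is conditional, no minimum AF count or precision is set for Aim 2, and the planned rhythm measure can hide poor AF detection. How many AF pairs will be obtained cannot be derived from the documents; the counts given here rest on assumed shares and rates.

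The 90% agreement with every AF episode missed, and the interval of 40% to 100% for 4 of 4, illustrate the mechanism for post-procedure pairs only. They are not a forecast for the trial. Aim 2 is secondary and the primary AFEQT comparison is unaffected, so this is a worthwhile low-cost improvement, with moderate confidence.

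**What to change.** **Protocol, Enrollment Procedure.** For cardioversion patients, set the order as: consent in Hugo, baseline AFEQT, randomisation, watch pairing, then one watch ECG before the procedure whenever a 12-lead is recorded for clinical care. Allow omission only where it would delay care, and record the reason. Portal linking follows, after the procedure if time is short. The Hugo account itself cannot be deferred, because consent is signed in it. Keep the post-procedure request as it is.

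**Protocol, Secondary Clinical Outcomes and item 12, and SAP 1.6.2.** Report rhythm agreement separately by 12-lead rhythm (AF, flutter, sinus) and by timing (before cardioversion, after cardioversion, follow-up), with the number of pairs and exact confidence intervals in each cell.

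No separate day-1 request is needed for ablation patients; the existing request for a watch ECG with any routine ECG, and the inclusion of ECGs during hospitalisation, largely cover it.

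**Cost.** Some wording, and a few staff minutes per watch-arm patient moved ahead of the procedure. The documents do not say that a 12-lead is always taken beforehand, so the gain depends on local practice. The downside is that some portal connections move to after the procedure. The Enrollment Procedure already allows this, with up to three contact attempts and then a letter, but there is a small risk that some are completed late or never. That matters because Hugo is the main source of the utilisation outcomes.
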